9.1.2. Inclusion criteria specific to the two untreated subjects

9.1.2.1 To qualify for candidacy as a subject who exposes untreated skin, an individual must be regarded as competent to do so by the Principal Investigator, must have participated in at least five prior Carroll-Loye repellent efficacy trials, or have participated in at least three such trials and have at least two years of experience as a college life sciences major, or be professionally employed in vector control services.

9.1.3 Exclusion criteria, all subjects:

- 9.1.3.1 Known to be hypersensitive to mosquito bites or exhibiting hypersensitivity during test
- 9.1.3.2 Known to be sensitive or showing sensitivity to any of the test product ingredients, after application.
- 9.1.3.3 Poor physical condition.
- 9.1.3.4 Unwilling to submit to brief query about personal condition.
- 9.1.3.5 Use of insect repellent within one day preceding the study.
- 9.1.3.6 Unwilling to refrain from use of perfumed products, alcoholic beverages or smoking after 9 PM the evening preceding the test and throughout the test.
- 9.1.3.7 Known to be pregnant or lactating. Pregnancy will be self-checked by each female volunteer on the morning of the repellent test using an OTC test kit provided by the Study Director. Results of each such test will be immediately verified by direct inspection by a female technician trained to make that assessment. Only volunteers scored as nonpregnant will be allowed to participate.
- 9.1.3.8 Unable to deliver the test materials to own left and right limbs.
- 9.1.3.9 Unable to see mosquitoes on skin or otherwise effectively monitor and remove mosquitoes that alight on skin.
- 9.1.3.10 Student or employee of the Study Director.
- 9.1.3.11 Does not regularly spend time in outdoor settings.
- 9.1.3.12 Withdraws from testing before receiving a confirming LIBe, when the total exposure duration is less than 90% of the mean of subjects who did not withdraw, and when not more than 2 of 10 subjects have so withdrawn.

If more that 2 of 10 subjects withdraw prematurely, those with the briefest participation will be replaced first. This exclusion factor is not automatically invoked if the Study Director ends exposures due to other factors, such as darkness; in such cases the data collected before termination may be sufficient to meet the study goals.

9.1.4 Number of Subjects and Rationale for Sample Sizes:

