At the field site, the subjects and researchers will gather in an area without biting mosquitoes. Subjects are instructed not to leave this area until guided by a researcher.

The technicians and other researchers who will assist subjects during the test will be introduced or reintroduced to the subjects. Subjects are instructed to call on them whenever they have questions. Each subject is given and must wear a head net, Tyvek coveralls, latex, nitrile or vinyl gloves in their size, and is given a mechanical aspirator to remove any mosquitoes that land on treated skin and attempt to bite (LIBe) once formal exposures begin. A researcher will remind subjects about how to identify LIBes and when and how to operate the aspirator. Subjects will be further instructed about protecting themselves from mosquito bites during the test, and about reporting when a mosquito that lands on skin treated with repellent.

Before a repellent is applied, subjects will be guided to wash the lower arms and/or legs with mild, fragrance-free soap, rinsing them with a spray of ethyl alcohol (35% in water), and then drying the limbs with a clean towel. A technician will then apply the test material to a forearm or lower leg of each subject, giving even, complete coverage of the skin. The amount of repellent to be applied to any limb will be calculated in advance for each subject. The dosing rate will be the product of the subject's limb surface area multiplied by the grand mean (mean of subject means) rate calculated in the dosimetry data analysis for the test material. Each subject will therefore be dosed at the same rate, even if their voluntary individual application rates might otherwise differ from the grand mean.

Treated subjects will be partnered into groups of two. A researcher will then guide subjects into the area of the field site in which mosquitoes are active. For a one-minute period, members of a partner pair will watch their own exposed limbs and those of their partner for mosquitoes that land. A technician will advise subjects when the one-minute period begins and ends. During exposure subjects will immediately remove any LIBing mosquitoes from the exposed skin with the aspirator. They may also use the plastic nozzle of the aspirator or a finger to interrupt any mosquito even more quickly. Partners will assist one another in removing mosquitoes as needed.

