Put on gloves. Practice using the switch on the aspirator handle to turn it on, and insert the sucking tube into the cage through the elastic cloth. Then place your arm with the bandage into the cage. About half or your forearm will be uncovered, with no insect repellent. Carefully watch the mosquito as it flies in the cage. Once it lands on your skin, watch carefully to see if it stops walking and places its needle-like mouth against your skin. You may move your arms to get better views and access to the mosquito. Once you observe a mosquito mouth touching your skin, you will immediately attempt to catch the mosquito in the plastic nozzle of the aspirator. You may practice as many times as you wish, with one and then two mosquitoes, and the researcher will be certain that your use of the mosquito aspirator is correct.

a. mosquitoes i. observing landings ii. mechanical aspiration (v. 1, 11 September 2006)

Carroll-Loye Biological Research

[name] [name] [contact] http://

http://www.carroll-loye.com/

Test Reference: LNX-001

CLBR Training Manual

§1.c. Practicing and performing dosimetry with a Pump Spray delivery system

A. Goals of exercise

- 1. Determine your preferred practices for applying ('self-dosing') a pump spray repellent to your arms and/or legs.
- 2. Assist technicians in measuring the amount of repellent that you apply when using your practices

B. General information

- 1. A technician will measure the surface area of your forearms and/or lower legs. He or she will introduce you to the repellent and its dispenser
- 2. You will work in open air, practicing applying the repellent. A technician will help you keep track of your preferred technique.
- 3. Using small gauze "bracelets" around your limbs to collect samples of repellent you spray on, you will apply repellent with your preferred practices several times. The bracelets will be quickly removed and weighed. You will thoroughly wash your limbs with a gently skin cleaner between each application of repellent.

C. Materials and equipment needed

- 1. Test materials
- 2. Latex or vinyl gloves (various sizes)
- 3. Bracelet dosimeters with nonabsorbent backing
- 4. Temperature, humidity and wind speed measuring devices
- 5. Written copy of the procedures for subjects to read
- 6. Flexible metric rule

US EPA ARCHIVE DOCUMENT

Carroll-Loye Biological Research

[name]	Davis, California 9	5616	[contact]	http://www.carroll-loye.	.com/
			- (

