In these instructions, the act of spraying a repellent on your limb will be termed 'spraying', 'application', or 'dispensing.'

You may work with the spray on your arms, legs, or both. The technician will inform you. Wash your limbs to be tested thoroughly with the provided cleanser and dry with a clean towel. Place new latex or vinyl gloves on each hand, choosing the size that fits you most snugly without being uncomfortably restricting or likely to tear when you put them on.

You will work with a technician who will assist you in measuring and recording your use of a repellent product in a pump spray delivery system.

First, familiarize yourself with the spray mechanism. Any actuation (pushing down on the pump plunger) of the spray must take place out-of-doors. Work at a distance of no less than 6 feet (1.9 meters) from other subjects. Do not dispense the spray at or near your face or anyone else's. Minimize inhalation of airborne spray while working.

Testing will take place out-of-doors during daylight hours at an air temperature (shade) above 10 $^{\circ}$ C (50 $^{\circ}$ F) and wind speed below 12 kph (7 mph), with no precipitation. The researcher or a technician will inform you when these conditions are not met and spraying of the repellents will cease until those conditions resume.

Dispense the spray on one limb designated by the technician. By successively moving the spray nozzle closer to and farther from the limb, identify a distance between nozzle and skin that seems most appropriate for effective application to the skin. The technician will measure and record that distance to the nearest centimeter on the provided datasheet.

Wash and dry the treated limb so that none of the repellent you have applied is visible on close inspection.

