Now, using the spray nozzle at or near the distance from the skin that you have just chosen to be effective for application, determine the minimum number of actuations (pumps of the pump spray). Depress the plunger fully each time, and count them aloud beginning with "1, 2, 3" etc. If you partially depress the plunger (rather than fully depress it) in order, e.g., to apply to a small skin area not covered be initial application, report that to the technician as a "half pump." Each partial depression should be so reported as it occurs. If on any given actuation material fails to be delivered, do not count that actuation. If a partial amount is delivered, estimate its volume as 'whole', 'half' or 'none' and report it as such. For 'none', simply resume counting at the next actuation that delivers material to the skin.

Report the count to the technician who will record it on the data sheet. The technician will also assist you in keeping track of whole versus half pumps. Discard your latex gloves, and wash both test limbs (arms or legs) with cleanser and dry them thoroughly with a towel.

Carroll-Loye Biological Research

[name] [name]

[contact]

http://www.carroll-loye.com/

Next, repeat the application procedure and collect the same data for the other limb. In doing so, try to be consistent with your use of the spray apparatus. If you are clear and confident about the distance from the limb that works best, pay enough attention to keep the nozzle in that general range while maintaining a natural delivery as you would use the product under normal personal use. Keep the nozzle aimed at the skin surface, and avoid orienting the containers in any ways that you determine, as you proceed with the trial, to interfere with delivery of the repellent to the skin surface.

Now move on to the Spray Sampling exercise described in the next section."

Spray Sampling²

Spray Sampling is the procedure by which the spray is "subsampled" with "patch dosimeters". Dosimeters of known surface area will be placed on subject lower limbs. These dosimeters will intercept a portion of the spray applied to the limbs. Be weighing dosimetry patches before and after treatment, the mass of the intercepted material can be calculated. The spray delivery systems will also be weighed before and after each application.

Spray sampling will be conducted according to the following procedure.

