The function of the "gauze bracelets" is to capture some of the spray that would otherwise reach your limb as you apply the test products. It is important that you do not alter the way in which you apply the materials in any intentional or substantial way from what you have already determined is your best procedure. The technician will review your results from your previous applications with you to assist you in repeating your general procedure (distance of nozzle to skin, number of spray pumps or aerosol sweeps) as you apply the materials to one of your limbs with the bracelets in place.

The gauze bracelets are narrow in order to minimize the extent to which your sensation of receiving the spray on the limb is changed. Do your best to proceed as if the sensation is not changed. In other words, attempt to avoid spraying additional material onto areas under the bracelets where the sensation of test material on the skin will be different or absent. Do not attempt to spray additional material directly onto a bracelet unless it is within an area that needs additional treatment. Again, attempt to repeat the procedure that you have already developed, and apply the materials "as if the bracelets were not there."

Put a new latex glove on each hand. Spray material onto one limb only. The technician will tell you to which limb to apply spray. You and the technician will collect the same data as previously.

After you have completed spraying, keep both limbs from making contact with any surface. All bracelets will be removed by a technician and taken for weighing.

Discard your gloves, and wash both limbs with cleanser and dry them thoroughly with a towel.

Repeat these procedures until you have made at total of three spray samples for the first limb, and three more for the second limb. If you have completed sampling on, e.g., both arms, the technician may then ask you to repeat the same measurement on both legs. Be sure to discard your gloves, and wash all limbs with cleanser and dry them thoroughly with a towel, including after the last application."

Carroll-Loye Biological Research

[name] [name] [contact] http://

http://www.carroll-loye.com/

Test Reference: LNX-001

CLBR Training Manual

§1c. Performing dosimetry with Lotion delivery systems

A. Goals of exercise

- 1. Determine your preferred practices for applying lotion repellents to your arms or arms and legs.

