"Put a new latex glove on each hand. You will apply lotion to one arm only. The technician will tell you to which arm to apply. You will begin with an amount that you suppose is about one half of what you will need to achieve thorough and uniform coverage. After spreading that around the lower part of your arm, you will apply more as needed to the area closer to your elbow. Begin by gently squeezing lotion from a tube with the cap open directly onto the horizontally-held surface of the opposite arm. Hand the tube to the technician. Using the index finger, spread the lotion as evenly as possible on all surfaces of the lower arm. Do not spread it onto the hand or beyond the marking on your wrist. If you have sufficient lotion left to spread it evenly and thoroughly toward the elbow, continue in the direction. Do note spread it beyond the elbow or past beyond the marking near the elbow. If you need more lotion to achieve thorough and even coverage, make sure you have wiped all repellent from your fingertips onto the skin and ask the technician to hand you the tube. Apply as much additional as you think you need, as before, but to complete the coverage. If you decide that you have applied more repellent that you would normally use to achieve thorough and even coverage, makes and dry the treated arm

d. Dosimetry (lotion only) i. practice ii. performance (v. 1, 1 December 2006)

¹ Limb dimensions and surface area (technical details):

The term 'limb' refers to the forearm and ¹the lower leg. The surface area of each limb is computed as the average of four evenly spaced circumferences (two peripheral, two central) of the forearm (elbow to wrist) or lower leg (back of knee to ankle) multiplied by the length of treatment area. The locale along the limb at which each circumference is taken will be recorded (for later use to place dosimeters) as the distance in centimeters from the distal margin of the site of the most distal circumference site (i.e., at wrist or ankle).

Carroll-Loye Biological Research

[name] [name] [contact] ht

http://www.carroll-loye.com/

so that none of the repellent you have applied is visible on close inspection, and begin again. Likewise, be careful to avoid dropping any lotion off of the arm, and if this happens, begin again as you would if you applied too much.

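### Both dosimetry procedures script latex gloves with no alternative at the sampling step, and no criterion asks about latex allergy: an avoidable, unscreened exposure

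*Protocol*

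**What the plan says.** Gloves are mentioned in several places in the protocol and its appended training manual, and the wording differs between them.

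- **Lotion dosimetry instructions (CLBR Training Manual, lotion exercise, part D):** "Put a new latex glove on each hand".
- **Spray dosimetry, sampling step (CLBR Training Manual §1.c, Spray Sampling):** "Put a new latex glove on each hand. Spray material onto one limb only".
- **Spray dosimetry, start of practice:** "Place new latex or vinyl gloves on each hand, choosing the size that fits you most snugly". The choice offered to the subject is one of size.
- **Spray dosimetry, end of practice:** "Discard your latex gloves, and wash both test limbs (arms or legs) with cleanser".
- **Materials lists (part C of both dosimetry exercises, and of the mosquito-handling exercise §1.a):** latex or vinyl.
- **Field test (Protocol 10.4.6):** "latex, nitrile or vinyl gloves in their size".

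On eligibility, Protocol 9.1.3.1 concerns hypersensitivity to mosquito bites, and 9.1.3.2 reads "Known to be sensitive or showing sensitivity to any of the test product ingredients, after application". Section 5.4 adds known allergy to repellents and common cosmetics. It describes study risk as coming from the test materials, biting arthropods and disease vectors. Neither section names latex or any glove material.

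**The concern.** Two of the procedures that subjects are told to follow specify latex at the point of data collection, although the equipment lists for the same exercises include a non-latex glove. Under 9.1.6.3, screening works by asking each candidate to address the listed exclusion criteria. An allergy that is not listed is therefore not systematically asked about. The stake is subject safety during dosimetry: exposure to a known type of allergen that the study does not need.

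A secondary possibility is misattribution. In the lotion exercise the subject spreads product over the forearm with the gloved index finger, so the glove touches the skin being treated. Under 9.5 any adverse skin reaction ends that subject's participation, and a glove reaction on the forearm could be recorded as a reaction to the product. The documents allow this but do not show that it would happen.

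**Working it through.** The plan states no figure on this point, so there is none to reproduce. The check compares the texts, then adds a calculation for scale only.

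**1. Is latex the only glove named at the sampling steps?** Yes, in the lotion instructions and in the spray sampling step. The spray script opens with latex or vinyl and then calls the gloves latex when they are discarded after practice. So the spray script conflicts with its own first gloving instruction, and both exercises conflict with their own materials lists.

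**2. Does any criterion cover latex?** No. 9.1.3.1 and 9.1.3.2 cover bites and product ingredients, and 5.4 adds repellents and cosmetics. Gloves are study equipment and fall under none of these.

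**3. How much exposure follows from a literal reading?**
- Spray sampling: three samples per limb, with gloves discarded and the procedure repeated each time. That is 3 glovings per limb, 2 × 3 = 6 for one pair of limbs, and 4 × 3 = 12 if both arms and legs are sampled.
- Lotion sampling: three applications per limb. Gloves are ordered once. Between applications the text asks only for the arm to be washed and dried. That is three gloved applications per limb, not three separate glovings.

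**4. How likely is it that a sensitive person is enrolled?**
- Input from the protocol: 10 dosimetry subjects per formulation (5.2, 9.1.4). The text does not say whether the two groups overlap, so n lies between 10 and 20 people.
- Assumed input: prevalence p of latex sensitivity. The documents give no value, so a range is shown.
- Formula: P(at least one) = 1 − (1 − p)^n.

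| Assumed p | n = 10 | n = 20 |
|---|---|---|
| 0.5% | 1 − 0.995^10 = 4.9% | 1 − 0.995^20 = 9.5% |
| 1% | 1 − 0.99^10 = 9.6% | 1 − 0.99^20 = 18.2% |
| 5% | 1 − 0.95^10 = 40.1% | 1 − 0.95^20 = 64.2% |

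These are chances that at least one sensitive person is among the dosimetry subjects. They are not chances of a reaction, which would also require that the person is given latex and does not speak up.

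**The case against.** The strongest reply is that this is loose wording. Vinyl is on the materials list for both exercises, the spray script's first instruction offers it, and the field test adds nitrile. Read together, the later references to latex may be shorthand for any disposable glove. This stands in part: the documents do not force latex on every subject. But a subject or technician following the lotion instructions or the spray sampling step literally finds only one material named.

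A second reply is that a person who knows of the allergy has chances to say so. Screening is a private interview (9.1.6.3), 9.1.3.4 provides for a brief query about personal condition, the spray script is read aloud with an invitation to ask questions, and the Study Director may refuse any candidate. This is fair, and it lowers the practical risk. It still leaves disclosure to the volunteer's initiative, because none of these steps mentions latex. The monitoring in 9.5 deals with a reaction once it appears and does not prevent one.

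Third, the consent form is not among the material available here, so whether it asks or warns about latex cannot be judged. That limits the claim to the eligibility criteria and scripts. A warning there would not remove the conflict between the scripts and their lists.

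A reader might infer that an allergic reaction is built into the study. The documents do not support that. They show an exposure that is unscreened and avoidable, and a listed alternative is at hand. A reader might also take 20 subjects as given, but that assumes no one does dosimetry for both products, which the protocol does not state.

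**Conclusion.** The point holds as a minor subject-safety and consistency defect. The lotion instructions and the spray sampling step name latex alone, against their own materials lists, and no criterion in 9.1.3 covers known latex allergy. A latex-allergic volunteer is eligible and, on a literal reading, is exposed repeatedly.

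The size of the problem depends on an assumed prevalence. With 1% to 5%, the chance of enrolling at least one sensitive person runs from about 10% (10 people, 1%) to 64% (20 people, 5%). The textual finding does not depend on that assumption. Nothing shows an effect on CPT, the dose estimate, the sample size or the analysis.

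**What to change.** - In the spray script (the discard instruction after practice, and the sampling step) and in the lotion instructions, replace latex with vinyl or nitrile.
- Bring the spray script's opening glove instruction and the materials lists of both dosimetry exercises into line with that wording.
- Where latex remains an option, as in the field test (10.4.6) and the mosquito-handling training (§1.a), either add known latex allergy to the items asked at screening under 9.1.3, or state that such subjects receive the non-latex gloves already listed.

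The cost is a wording change. Vinyl is already listed for both dosimetry exercises and nitrile for the field test. No procedure, sample size or analysis changes. It should be made before dosimetry begins, since that is where the latex-only instructions apply.
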